7.10.4 Pharmaceutical and Therapeutic Background

The importance of intact immune surveillance in controlling outgrowth of neoplastic transformation has been known for decades. Accumulating evidence shows a correlation between tumour-infiltrating lymphocytes (TILs) in cancer tissue and favourable prognosis in various malignancies. In particular, the presence of CD8+ T-cells and the ratio of CD8+ effector T-cells / FoxP3+ regulatory T-cells seems to correlate with improved prognosis and long-term survival in many solid tumours.

The PD-1 receptor-ligand interaction is a major pathway hijacked by tumours to suppress immune control. The normal function of PD-1, expressed on the cell surface of activated T-cells under healthy conditions, is to down-modulate unwanted or excessive immune responses, including autoimmune reactions. PD-1 (encoded by the gene *Pdcd1*) is an Ig superfamily member related to CD28 and CTLA-4 which has been shown to negatively regulate antigen receptor signalling upon engagement of its ligands (PD-L1 and/or PD-L2). The structure of murine PD-1 has been resolved. PD-1 and family members are type I transmembrane glycoproteins containing an Ig Variable-type (V-type) domain responsible for ligand binding and a cytoplasmic tail which is responsible for the binding of signalling molecules. The cytoplasmic tail of PD-1 contains 2 tyrosine-based signalling motifs, an immunoreceptor tyrosine-based inhibition motif (ITIM) and an immunoreceptor tyrosine-based switch motif (ITSM). Following T-cell stimulation, PD-1 recruits the tyrosine phosphatases SHP-1 and SHP-2 to the ITSM motif within its cytoplasmic tail, leading to the dephosphorylation of effector molecules such as CD3 ζ , PKC θ and ZAP70 which are involved in the CD3 T-cell signalling cascade. The mechanism by which PD-1 down modulates T-cell responses is similar to, but distinct from that of CTLA-4 as both molecules regulate an overlapping set of signalling proteins. PD-1 was shown to be expressed on activated lymphocytes including peripheral CD4+ and CD8+ T-cells, B-cells, T regs and Natural Killer cells. Expression has also been shown during thymic development on CD4-CD8- (double negative) T-cells as well as subsets of macrophages and dendritic cells. The ligands for PD-1 (PD-L1 and PD-L2) are constitutively expressed or can be induced in a variety of cell types, including non-hematopoietic tissues as well as in various tumours. Both ligands are type I transmembrane receptors containing both IgV- and IgC-like domains in the extracellular region and contain short cytoplasmic regions with no known signalling motifs. Binding of either PD-1 ligand to PD-1 inhibits T-cell activation triggered through the T-cell receptor. PD-L1 is expressed at low levels on various non-hematopoietic tissues, most notably on vascular endothelium, whereas PD-L2 protein is only detectably expressed on antigen-presenting cells found in lymphoid tissue or chronic inflammatory environments. PD-L2 is thought to control immune T-cell activation in lymphoid organs, whereas PD-L1 serves to dampen unwarranted T-cell function in peripheral tissues. Although healthy organs express little (if any) PD-L1, a variety of cancers were demonstrated to express abundant levels of this T-cell inhibitor. PD-1 has been suggested to regulate tumour-specific T-cell expansion in participants with melanoma (MEL). This suggests that the PD-1/PD-L1 pathway plays a critical role in tumour immune evasion and should be considered as an attractive target for therapeutic intervention.

Pembrolizumab is a potent and highly selective humanized monoclonal antibody (mAb) of the IgG4/kappa isotype designed to directly block the interaction between PD-1 and its ligands, PD-L1 and PD-L2. Keytruda™ (pembrolizumab) has recently been approved in the United States for the treatment of patients with unresectable or metastatic melanoma and disease progression following ipilimumab and, if BRAF V600 mutation positive, a BRAF inhibitor.

7.10.5 Preclinical and Clinical Trial Data

Refer to the Investigator's Brochure for Preclinical and Clinical data.

7.11 Rationale for the Trial and Selected Participant Population

This study will evaluate the safety profile, efficacy and biological effects of the combination of pembrolizumab, a T cell checkpoint inhibitor and SABR for oligometastatic renal cancer (1-5 sites of disease). Our hypothesis is that this treatment combination will have a safety profile that is clinically acceptable and demonstrate anti-tumour efficacy.

The sample size of 30 is pragmatic. It is recognized that the findings of this study will serve as the basis for larger randomized studies in the future. Whilst previously, patients with oligometastatic renal cancer have been thought to be incurable, long term survival has been reported with judicious use of surgery or SABR treatment. We hypothesize that augmentation of immunity in this subgroup of patients may enhance long-term control of the disease.

Whilst the overlapping toxicities of SABR and pembrolizumab are not yet fully understood, none are expected as the toxicity profiles are due to non-overlapping mechanisms. Safety will be monitored carefully throughout the trial in all patients.

7.12 Rationale for Selection of Immunotherapy to Combine with SABR in the Oligometastatic RCC Cohort

In the context of local therapies for patients with oligometastatic disease, the major site of disease recurrence after local therapies such as surgery or surgery is distant. In large prospective database studies, patients with a single site of metastasis have significantly longer survival and lower probability of disease recurrence than those with two or more, however, the majority of patients with a solitary metastases still recurred with distant disease. In a prospective study published in the Lancet Oncology of 1194 patients by Yamamoto et al. [75] of patients with brain metastases treated with stereotactic radiotherapy, patients with a solitary metastasis had a significantly longer survival ($p < 0.001$) than patients with 2 or more metastases. In patients with RCC the median survival for patients with a solitary metastasis was 16.3 months versus 13.7 months in those patients with 2-4 metastases. Similarly, the large multinational registry study of 5206 patients with pulmonary metastases by Pastorino et al. [76] also addressed the number of metastases as a prognostic factor for survival. Patients with a single metastasis had significantly better survival than those with two or more metastases (Figure 1). The 5-year survival was 43% for single lesions and 27% for four or more lesions ($p < 0.001$), however there was no statistically significant difference between patients with 2-3 metastases versus 4 or more.

Overall, this suggests that in patients with oligometastases, some form of systemic therapy may be useful in order to limit the risk of progression of occult micrometastatic disease. However there is no proven benefit of adjuvant systemic TKI therapy in the setting of renal cell carcinoma. Systemic targeted agents (TKI) have not been proven to prolong survival in patients in the primary setting after nephrectomy, indicating that it is incapable of totally eradicating any micrometastatic disease. This evidence could be extrapolated to those patients treated with local therapy SABR for oligometastatic disease, as there is no synergistic effect with radiation and TKIs at distant micrometastatic sites. Pembrolizumab not only can potentiate the effectiveness of radiation at the irradiated tumours, it has the potential to

evoke a sustained anti-tumour immune response at distant sites, which has resulted in a proportion of patients observed to have long-term disease control and perhaps even cure.

7.13 Rationale for Dose Selection/Regimen/Modification of pembrolizumab

As of the data cut-off dates for this IB (18-Apr-2014 for P001 melanoma subjects, 29-Aug-2014 for P001 NSCLC subjects, 12-May-2014 for P002, and 30-Nov-2014 for other protocols), the safety and efficacy of pembrolizumab treatment in subjects with hematologic malignancies and solid tumors have been evaluated in 18 ongoing, Merck-sponsored clinical trials: P001, P002, P006, P010, P011, P012, P013, P021, P022, P023, P024, P025, P028, P029, P030, P041, P045, and P055. An outline of selected studies and design are described below.

P001 was an open-label, Phase I, first-in-human (FIH) study of IV pembrolizumab in subjects with progressive locally advanced or metastatic carcinomas, especially melanoma or NSCLC. Part A of the study involved dose escalation that used a traditional 3+3 design. Cohorts of 3 to 6 subjects were enrolled sequentially at escalating doses of 1, 3, or 10 mg/kg administered Q2W. Once the dose escalation was completed, additional subjects were enrolled into Parts A1 and A2 to further characterize the PK and pharmacodynamics of pembrolizumab. In Parts B and D, subjects with metastatic melanoma were enrolled to assess the safety and antitumor activity of pembrolizumab. Additionally, Part B explored 3 different dose regimens in subjects with metastatic melanoma: 10 mg/kg Q2W, 10 mg/kg Q3W, and 2 mg/kg Q3W. In Part C, subjects with NSCLC (with prior systemic therapy) were enrolled at 10 mg/kg Q3W to assess the tolerability, safety, and antitumor activity of pembrolizumab in NSCLC. In Part F, subjects with NSCLC in Cohort F-1 (without prior systemic therapy) and Cohort F-2 (with prior systemic therapy), whose tumors expressed PD-L1, were enrolled at 10 mg/kg Q2W and 10 mg/kg Q3W to characterize the tolerability, safety, and antitumor activity of pembrolizumab. A small cohort of previously treated subjects with NSCLC and at least 2 lines of systemic therapy, whose tumors did not express PD-L1, were enrolled and treated at a dose of 10 mg/kg Q2W in Cohort F-2. In Cohort F-3, previously treated subjects with NSCLC whose tumors express PD-L1 were enrolled at 2 mg/kg Q3W to better characterize the efficacy, safety, and antitumor activity of pembrolizumab. Each of the 2 disease specific cohorts (melanoma and NSCLC) were enrolled to confirm tolerability and evaluate tumor response to pembrolizumab.

P006 was a multicenter, worldwide, randomized, controlled, open-label, 3-arm pivotal Phase III study of 2 dosing regimens of IV pembrolizumab versus IV IPI in subjects with unresectable or metastatic melanoma who had not received prior IPI treatment. Subjects were randomized in a 1:1:1 ratio to receive pembrolizumab at 10 mg/kg Q2W, 10 mg/kg Q3W, or IPI at 3 mg/kg Q3W for a total of 4 doses.

P010 is a multicenter, worldwide, randomized, adaptively designed Phase II/III trial of IV pembrolizumab at 2 dosing schedules versus docetaxel in subjects with NSCLC with PD-L1 positive tumors, who have experienced disease progression after platinum-containing systemic therapy. Subjects were randomized in a 1:1:1 ratio to receive pembrolizumab 10 mg/kg Q3W, 2 mg/kg Q3W, or docetaxel 75 mg/m² Q3W.

P011 was an open-label, nonrandomized, multicenter Phase I study of pembrolizumab monotherapy in Japanese subjects with advanced solid tumors and in combination with cisplatin/pemetrexed and carboplatin/paclitaxel in subjects with advanced NSCLC in Japan. In Part A (monotherapy, 3+3 design), subjects with advanced solid tumors received escalating doses of pembrolizumab 2 mg/kg Q2W (dose level 1) or 10 mg/kg Q2W (dose level 2). In Part

B (combination, 3+6 design), subjects with advanced NSCLC receive pembrolizumab 10 mg/kg Q3W in combination with either cisplatin/pemetrexed (Cohort 1) or carboplatin/paclitaxel (Cohort 2) are to be enrolled.

P012 was a multicenter, nonrandomized, multi-cohort Phase Ib trial of pembrolizumab in subjects with PD-L1 positive advanced solid tumors. All subjects receive pembrolizumab 10 mg/kg Q2W. Cohort A enrolled subjects with triple negative breast cancer; Cohorts B and B2 enrolled subjects with squamous cell carcinoma of the head and neck; Cohort C enrolled subjects with urothelial tract cancer of the renal pelvis, ureter, bladder, or urethra; and Cohort D enrolled subjects with adenocarcinoma of the stomach or gastroesophageal junction.

P021 was a multicenter, open-label Phase I/II study of IV pembrolizumab at 2 dosing schedules in combination with chemotherapy or immunotherapy in subjects with locally advanced or metastatic NSCLC.

P022 is a multicenter, worldwide, Phase I/II 3-part trial of IV pembrolizumab in combination with oral dabrafenib and/or trametinib in subjects with advanced or metastatic melanoma. Part 1 is a non-randomized, multi-site, open-label portion of the study using a traditional 3+3 design to evaluate safety, tolerability, and dosing of pembrolizumab (MK) in combination with dabrafenib (D) and trametinib (T) in BRAF mutation-positive (V600 E or K) melanoma subjects. Additionally in Part 1, dosing of pembrolizumab in combination with trametinib only (MK+T) will be explored in BRAF mutation-negative (without V600 E or K) melanoma subjects, to evaluate safety, tolerability, and efficacy of MK+T in Part 2 in this population. Part 2 is a non-randomized, multisite, open-label portion of the study using an expansion cohort to further evaluate safety and confirm dose of MK+D+T. Also in Part 2, an expansion cohort will be used to further evaluate safety and preliminary efficacy in the MK+T combination. Part 3 is a randomized (1:1), active-controlled, multi-site, 2-arm study of the confirmed dose of the triplet combination (MK+D+T) versus placebo (PBO) in combination with D+T (PBO+D+T).

P029 is a multicenter, open-label, 3-part Phase I/II trial of IV pembrolizumab in combination with subcutaneous Pegylated Interferon Alfa-2b (PEG-IFN) or IV IPI in subjects with advanced or metastatic melanoma or renal cell carcinoma. Part 1A, the Phase I portion of the trial, will define the preliminary MTD or MAD of pembrolizumab + PEG-IFN (Group A) and pembrolizumab + IPI (Group B), and confirm the tolerability of these treatment doublets.

P030 is a multisite, worldwide, expanded access program for subjects with metastatic melanoma who have limited or no treatment options. Subjects must have progressed after prior systemic therapy, including standard-of-care agents which include IPI and a BRAF/MEK inhibitor when indicated. Subjects cannot be eligible for an available pembrolizumab clinical trial or have participated in a pembrolizumab clinical trial. Subjects are evaluated for safety at baseline and before each cycle of treatment with pembrolizumab 2 mg/kg/Q3W. Subjects are treated until progression of disease or until the subject has received up to 2 years of treatment.

P045 is a randomized, active-controlled, multisite, open-label, Phase III trial to evaluate the efficacy of treatment with pembrolizumab versus paclitaxel, docetaxel, or vinflunine in subjects with metastatic or locally advanced/unresectable urothelial cancer that has recurred or progressed following platinum-containing chemotherapy. Subjects are randomized in a 1:1 ratio to receive pembrolizumab 200 mg Q3W or the Investigators' choice of paclitaxel 175

mg/m² Q3W, docetaxel 75 mg/m² Q3W, or vinflunine 320 mg/m² Q3W. The study also evaluates the safety and tolerability profile of pembrolizumab in subjects with recurrent/progressive metastatic urothelial cancer.

P055 is a multicenter, unblinded, open-label, single-cohort, Phase II trial to determine the safety, tolerability, and antitumor activity of a 200 mg Q3W dose of pembrolizumab in subjects with recurrent and/or metastatic head and neck squamous cell carcinoma who have progressed on platinum and cetuximab therapy. Antitumor activity is also assessed in the subset of subjects for whom a biopsy sample is determined to be PD-L1 positive.

The choice of the 200 mg Q3W as an appropriate dose for the switch to fixed dosing is based on simulations performed using the population PK model of pembrolizumab showing that the fixed dose of 200 mg every 3 weeks will provide exposures that 1) are optimally consistent with those obtained with the 2 mg/kg dose every 3 weeks, 2) will maintain individual patient exposures in the exposure range established in melanoma as associated with maximal efficacy response and 3) will maintain individual patients exposure in the exposure range established in melanoma that are well tolerated and safe.

A fixed dose regimen will simplify the dosing regimen to be more convenient for physicians and to reduce potential for dosing errors. A fixed dosing scheme will also reduce complexity in the logistical chain at treatment facilities and reduce wastage.

A favourable safety profile and preliminary evidence of clinical activity led to the design of a multi-dose trial of nivolumab (anti-PD-1) in 296 patients, confirming antitumor efficacy in melanoma, RCC and NSCLC [77]. In this study, cumulative response rates were 18% for patients with non-small-cell lung cancer (NSCLC), 28% for patients with melanoma, and 27% (9 of 33 patients) for patients with RCC. Recently, in 2015, the results of a randomized, dose-ranging phase II trial of nivolumab in 168 pretreated metastatic RCC patients were published. The median progression-free survival was 2.7 months in the 0.3 mg/kg group, 4.0 months in the 2 mg/kg group, and 4.2 months in the 10 mg/kg group. The median overall survival was 18.2 months in the 0.3 mg/kg group, 25.5 months in the 2 mg/kg group, and 24.7 months in the 10 mg/kg group. More than 50% of responders with all doses had objective responses lasting more than 12–20 month [78].

The CheckMate 025 study is a phase III randomized trial of nivolumab versus everolimus in patients with advanced RCC [ClinicalTrials.gov identifier: NCT01668784]. Patients who received one or two prior anti-angiogenic therapies for advanced RCC (but not more than three total previous therapies) were randomized to receive nivolumab at 3 mg/kg every 2 weeks versus everolimus until disease progression or unacceptable side effects. The primary endpoint of this study was overall survival. In July 2015, the independent Data Monitoring Committee concluded that the study had met its primary endpoint. While full results remain forthcoming, this study will likely establish anti-PD-1 as a new standard of care for previously treated patients with metastatic kidney cancer.

7.14 Rationale of Endpoints Definition

Primary Endpoint:

Safety (acute and long term) will be evaluated using CTCAE version 4.03 in all patients who have received at least one SABR treatment and one dose of pembrolizumab. Acute adverse events (AE) are defined as AEs occurring from the time of first SABR treatment to 30 days post

end of pembrolizumab treatment and long term AE are defined as AEs occurring after 30 days post end of pembrolizumab treatment.

Secondary Endpoints:

To evaluate effectiveness of the treatment combination, using the following measures:

- a) Overall survival (OS), time to local progression (TTLP), distant progression free survival (DPFS) and overall response rates
 - i. OS will be measured from the date of commencement of SABR treatment to the date of death from any cause.
 - ii. TTLP will be measured from date of commencement of SABR treatment to the date of first local progression. Death and commencement of a further course of systemic therapy will be considered as censoring events.
 - iii. DPFS will be measured from the date of commencement of SABR treatment to the date of first distant progression at site not documented at registration, or date of death from any cause for patients without distant progression. Commencement of second course of a further course of systemic therapy will be considered as censoring event.
- b) Overall response is defined as complete response or partial response, measured using RECIST 1.1 criteria. The RECIST definition of complete response has been modified to include disappearance of the target tumor radiographically or complete metabolic response. The primary is excluded from the evaluation of the overall response.
- c) Disease control is defined as complete response or partial response at any time after treatment commencement or stable disease for at least 6 months, measured using RECIST 1.1 criteria. The RECIST definition of complete response has been modified to include disappearance of the target tumor radiographically or complete metabolic response. The primary is excluded from the evaluation of the disease control.
- d) Pain will be evaluated using the Numerical Pain Rating Scale at the following time points: pre-conventional radiotherapy treatment (if CRT performed), pre-SABR treatment, prior to each cycle of pembrolizumab, then 3 monthly until 24 months after the end of SABR treatment.

Exploratory Endpoints

A number of translational endpoints will be evaluated including:

1. PD-L1 expression in primary tumour and metastatic lesions using immunohistochemistry.
2. Tumour infiltrating lymphocytes (TILs) using a previously defined method at primary tumour and metastatic lesions.
3. Blood samples will be collected at multiple timepoints (prior to radiotherapy, prior to each pembrolizumab administration, at disease progression (if this occurs) and at 9, 12 and 24 months post SABR treatment). These will be analysed for the following (this is a non-exhaustive list):
 - i. Absolute lymphocyte counts using a blood analyser.
 - ii. The presence of CD8+ T cells by flow cytometric analysis.
 - iii. Presence of tumour reactive T cells. These may include markers for HLA-DR, CD4+, CD8+ T cells, PD-1, TIM-3 signifying antigen presentation and experience.

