2 SCHEDULE OF EVENTS

Table 1: Schedule of Events

Trial Period:	Screening Phase	Radiotherapy	Treatment Cycles		Safety Follow-up	Follow-up ¹⁷	Progression (Upon first progression)
Treatment Cycle/Title:	Screening	SABR±CRT ³	Day 1 Cycle 1	Day 1 Cycle 2-8			
Scheduling Window (Days):	-35 to -1	Commence within 4 weeks of registration ³	5 days post SABR ± 3 days	21 days post previous cycle Day 1 ± 3 days	30 days from date of last dose of pembrolizumab ± 3 days	3 months from SABR ± 14 days	
Clinical/Administrative Assessments							
Informed Consent	X						
Inclusion/Exclusion Criteria	X						
Demographics and Medical History	X						
Disease Specific Medical History	X						
SINS score for Spinal Targets	X						
Full Physical Examination	X		X	X			
Directed physical Examination						X	
Vital Signs ¹ and Body Measurements	X		X	X		X	
ECOG Performance Status	X		X	X		X	
Review Adverse Events ²	X		X	X	X	X	X
Radiotherapy planning	X						
Trial Treatment Administration – SABR ³		X					
Trial Treatment Administration – Pembrolizumab ⁴			X	X			See section 10.6
Review Prior/Concomitant Medications	X		X	X			
Numerical Pain Rating Score		X	X	X		X	
New Anti-Cancer Therapy Status / Second phase pembrolizumab					X	X	X
Survival Status ¹⁸						X	
Laboratory Procedures/Assessments: analysis performed by LOCAL laboratory							

Trial Period:	Screening Phase	Radiotherapy	Treatment Cycles		Safety Follow-up	Follow-up ¹⁷	Progression (Upon first progression)
Treatment Cycle/Title:	Screening	SABR±CRT ³	Day 1 Cycle 1	Day 1 Cycle 2-8			
Scheduling Window (Days):	-35 to -1	Commence within 4 weeks of registration ³	5 days post SABR ± 3 days	21 days post previous cycle Day 1 ± 3 days	30 days from date of last dose of pembrolizumab ± 3 days	3 months from SABR ± 14 days	
Pregnancy Test ⁵ – Urine or Serum β-HCG	X		X	X			
Haematology ⁶	X		X	X		As clinically indicated	
Chemistry ^{7,8}	X		X	X			
T3, FT4 and TSH ⁹	X		X	X			
PT/INR and aPTT ¹⁰	X						
HIV, Hepatitis B and C ¹¹	X						
Tumour Evaluation							
Tumour assessment by CT scan or MRI ¹² (Chest, Abdo, Pelvis) reported as per RECIST 1.1	X				X (Every 3 months from SABR)		
CT scan (Brain) (if clinically indicated) ¹²	X			X (Cycle 4 & 8 only)		As clinically indicated	
Whole body bone scan (if clinically indicated) ¹²	X			X (Cycle 4 & 8 only)		As clinically indicated	
Metastatic FFPE Biopsy ¹³	X					X (month 9 only)	X
Primary Surgery FFPE sample ¹⁴	X						
Blood Serum Sample		X	X	X		X (9, 12 and 24 months)	X

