11. HIV, Hepatitis B and C tests only need to for those patients at risk of prior or current active infection as determined by the investigating clinician. These tests only need to be performed within 7 days of study registration only.

Tumour evaluation - Screening CT and WBBS should be completed within 35 days prior to study registration.

12. Clinical and radiological tumour assessments will be performed by CT scan (or MRI as required if tumour is in extremity) at screening and every 3 monthly post-SABR treatment until the last evaluable patient completes 12 months of follow-up.

Brain CT will be performed if clinically indicated at the same time points. Whole body bone scans will be performed at 3 and 6 months post SABR treatment only in patients with bone disease at baseline and as clinically indicated at the 3 monthly post SABR treatment follow-up visits.

Disease progression should be confirmed with repeat imaging 4 to 6 weeks later by the same imaging modality or by biopsy. If PET-CT scan has been done clinically this can be used for confirmation of disease progression provided the CT component of the PET-CT scan is of adequate resolution.

Biological Evaluations

13. If an archival biopsy specimen from a metastases exists then this should be submitted (block or unstained slides). An optional biopsy of metastatic site will be performed at 9 months post completion of SABR, if feasible. This will ideally be the same site as biopsied before trial related treatments (also optional). In event of disease progression - A sample from the metastatic site, if feasible, is requested. If taken, one-two formalin-fixed, paraffin-embedded (FFPE) tumour blocks should be requested.

14. If the patient had surgery for the primary tumour, one tumour block from resection should be submitted.

15. Prior to radiotherapy, first dose of pembrolizumab (all cycles), at disease progression (if this occurs) and at 9, 12 and 24 months post SABR treatment, whole blood samples will be collected for immune endpoints (refer to the RAPPORT Laboratory Manual for details on collection and processing).

16. EDTA whole blood sample (refer to the RAPPORT Laboratory Manual for details for collection and processing).

Follow-Up Visits

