3 TRIAL SUMMARY

Title	Stereotactic R adiotherapy and A nti- P D1 antibody (P embrolizumab) for O ligometastatic R enal T umours
Abbreviated Title	RAPPOR
Trial Phase	Phase 1b/II
Clinical Indication	Patients with oligometastatic renal cancer (1-5 metastases) considered safe for stereotactic ablative body radiosurgery (SABR)
Trial Type	Prospective, single arm study
Route of administration	SABR treatment (18Gy-20Gy/1#) followed by 200mg pembrolizumab (MK-3475) IV once every 3 weeks for a total of 8 cycles (~6 months).
Trial Blinding	Open label
Number of trial subjects	30 evaluable* patients in total.
Estimated enrolment period	24 months
Estimated duration of trial	36 months
Duration of Participation	~20 months

* Evaluable patients are defined as participants who complete at least one SABR treatment and receive at least one dose of study drug (18-20Gy/1# to at least one lesion with at least one dose of pembrolizumab).

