10.1.14 Tumour Imaging and Assessment of Disease

Imaging will be performed as per below:

- All pre-registration/screening investigations (CT Scan and WBBS) should be completed within 35 days prior to study registration.
- Clinical and radiological tumour assessments (post study registration) will be performed by CT scan or MRI (Chest, Abdo, Pelvis, and Brain if clinically indicated) reported with RECIST 1.1 (if possible) unless evidence of progression earlier or clinically inappropriate. WBBS will be performed at 3 and 6 months post SABR treatment in patients with bone disease detected at baseline, and/or if clinically indicated at any of the 3 monthly follow-up visits. Follow-up visits will continue until the last evaluable patient completes 12 months of follow-up.

Disease progression, as per RECIST 1.1, should be confirmed with repeat imaging 4 to 6 weeks later by the same imaging modality or by biopsy. If PET-CT scan has been done this can be used for confirmation of disease progression provided the CT component of the PET-CT scan is of adequate resolution. Complete response includes disappearance of the target tumor radiographically or metabolically (standardized uptake value = 0 when the pre-treatment PET, if done, was metabolically active). Efficacy will be evaluated by time to local progression as well as failures in other sites.

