11.2.6 Response analysis

All tumour response measurements (pre- and post-treatment) must be recorded using the definitions of RECIST 1.1 following SABR treatment. RECIST assessments will take into account post-treatment inflammatory processes that occur after SABR treatment in pulmonary and liver tissues.

DCR, ORR at 3, 6, 12 and 24 months and best overall response will be described as percentages with exact 95% confidence intervals for: a) DCR; b) ORR at 3, 6, 12 and 24 months and c) best overall response. If at least one patient has non-target disease only with response classified as non-CR/non-PD, then the response rate of CR will be reported instead of CR+PR.

The change in lesions size over time will be displayed graphically on the subset of lesions with measurable disease at baseline, with each lesion represented as a separate line and line colour representing the radiotherapy modality (SABR or conventional RT).

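### Complete response can be reached through a PET scan that is not scheduled, so ORR partly reflects who happened to be scanned; report a CT/MRI-only version beside it

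*Combined protocol and SAP*

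**What the plan says.** Section 7.14 states, under both b) overall response and c) disease control: "The RECIST definition of complete response has been modified to include disappearance of the target tumor radiographically or complete metabolic response". It gives no threshold, baseline-scan requirement, timing or reader for the metabolic part. The same section also leaves the primary tumour out of both assessments.

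Section 10.1.14 describes the metabolic route as disappearance "metabolically (standardized uptake value = 0 when the pre-treatment PET, if done, was metabolically active". The baseline PET is therefore itself optional.

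Table 1 in Section 2 schedules CT or MRI ("Chest, Abdo, Pelvis) reported as per RECIST 1.1") at screening and every 3 months from SABR, with brain CT and bone scan where indicated. It has no PET row. Footnote 12 mentions PET only as something that may have been done, and for a different purpose: "If PET-CT scan has been done clinically this can be used for confirmation of disease progression".

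Section 11.2.1 defines the response-evaluable set by CT/MRI at the visit. Section 11.2.6 plans exact 95% confidence intervals for DCR, for ORR at 3, 6, 12 and 24 months, and for best overall response. It refers to RECIST 1.1 definitions and does not mention PET. It also contains a switch: when one or more patients have only non-target lesions and are graded non-CR/non-PD, "then the response rate of CR will be reported instead of CR+PR". No section plans a CT/MRI-only analysis.

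**The concern.** Every patient is assessed by CT or MRI, but only those with a clinically ordered PET can reach CR metabolically. The documents do not say who gets PET, when, or how a patient without a baseline PET is handled. In response classification the metabolic route only moves a patient up: it can turn partial response (PR) or stable disease (SD) into CR, and nothing in the definition lets it take a CR away. Two patients with identical CT findings can therefore be classified differently because one was scanned.

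Response is descriptive here, so the reported percentage is the result. Section 11.1 says evidence of efficacy would support moving to a larger randomized study. Section 7.13 quotes a 27% (9 of 33) response rate in renal cell carcinoma from a multi-dose nivolumab trial, which readers may set beside this trial's ORR. A rate that mixes CT-based and opportunistic PET-based CR cannot be compared cleanly with a size-based one.

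**Working it through.** **Inputs.** The denominator is 30 (Trial Summary: "30 evaluable* patients in total"). The interval method is the exact 95% CI of 11.2.6. The DCR rule is from 7.14: "Disease control is defined as complete response or partial response at any time after treatment commencement or stable disease for at least 6 months". The documents give no PET frequency, metabolic response rate, or expected ORR or DCR.

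**Step 1: the plan's own interval.** There is no planned ORR figure to reproduce, but Table 8 uses the same n and an exact interval. For x events in n, the Clopper-Pearson limits are the 0.025 quantile of Beta(x, n−x+1) and the 0.975 quantile of Beta(x+1, n−x). For x = 12, n = 30 they are 22.7% and 59.4%, which round to the stated 23% and 59%. All 12 rows of Table 8 match.

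**Step 2: what one metabolic CR changes.**

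| Category by size | ORR (CR+PR) | DCR | CR rate and best overall response |
|---|---|---|---|
| PR | unchanged | unchanged | changes |
| SD for 6 months or more | +1/30 | unchanged | changes |
| SD for under 6 months | +1/30 | +1/30 | changes |
| Progression by size | +1/30 | +1/30 | changes |

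Here 1/30 = 3.3 percentage points. If the CR-only switch in 11.2.6 is triggered, the PR row also moves the reported response rate by 1/30.

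**Step 3: illustration on assumed counts.** Suppose 12 of 30 respond by size and k patients with SD by size are called metabolic CR, so that ORR = (12 + k)/30.

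| k | ORR | Exact 95% CI |
|---|---|---|
| 0 | 40.0% | 22.7–59.4 |
| 1 | 43.3% | 25.5–62.6 |
| 3 | 50.0% | 31.3–68.7 |
| 6 | 60.0% | 40.6–77.3 |

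The increment does not depend on the base rate: from 9/30, k = 6 takes ORR from 30.0% to 50.0%.

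**Step 4: dependence on scanning.** Suppose 6 patients with SD by size would qualify metabolically if scanned, and a fraction f of them is scanned. Expected ORR is (12 + 6f)/30, which is 40% at f = 0, 50% at f = 0.5 and 60% at f = 1. The tumours and the treatment are the same in each case; only the scanning differs. With CR judged on CT/MRI alone, ORR is 40.0% whatever f is.

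**Step 5: the two wordings.** Section 7.14 names a complete metabolic response and sets no threshold. Section 10.1.14 sets an uptake value of 0 and refers to a metabolically active pre-treatment PET. Neither section refers to the other.

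**The case against.** A metabolic supplement is a defensible choice. Section 11.2.6 itself recognises that inflammation after SABR affects reading in lung and liver. CT/MRI is scheduled for everyone and determines who is response-evaluable, so PET adds to the scheduled scan and does not replace it. Response is a secondary, descriptive outcome with no threshold or test. If an uptake value of exactly 0 is applied strictly, few upgrades may occur. All of this stands. It limits the importance of the point but does not remove the uneven access to CR.

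A reader might also infer more than the documents support:

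- **That there are two conflicting metabolic criteria.** Section 10.1.14 can be read as the working rule for the term that 7.14 leaves undefined. What is missing is the link between them.
- **That DCR is inflated as much as ORR.** PR, and SD of at least 6 months, already count as disease control, so most upgrades would leave DCR unchanged.
- **That the CR-only switch makes the metabolic rule the whole endpoint.** The switch has a specific trigger. Eligibility requires measurable disease, so it should be uncommon. Radiographic CR would still count.
- **That a particular inflation can be predicted.** Any number of upgraded patients is an assumption.

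**Conclusion.** The point holds for ORR, the CR rate and best overall response, and narrowly for DCR. As written, only patients scanned for clinical reasons have an additional, upward-only route to CR, and no planned analysis shows the result without it. The size is 3.3 points of ORR per patient with SD by size who is called a metabolic CR, taking 30 as the denominator. Where fewer patients are response-evaluable at a visit, each counts for more (1/n). The total effect cannot be derived, because PET coverage and the frequency of metabolic CR are not given; the range of 0 to 20 points for k = 0 to 6 is illustrative only. The primary safety endpoint and the sample size are not affected. Which version should lead is open to debate. What is needed is that both can be seen.

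**What to change.** In 11.2.6, report ORR, DCR and best overall response for all patients in the analysis with CR judged on CT/MRI only, alongside the PET-modified version. Keep the exclusion of the primary tumour and the allowance for post-SABR inflammation in both. A switch to wholly unmodified RECIST 1.1 is not needed and, read literally, would remove those two features as well. Beside the two results, give the number of patients with a baseline PET, the number with a follow-up PET, and the number reclassified by PET alone.

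In 7.14 b) and c), refer to the single metabolic criterion in 10.1.14 so that one rule applies throughout.

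The cost is wording in 7.14 and 11.2.6 and one extra table row. No new scans or visits are needed. The CT/MRI-only rate may be lower than the PET-modified one.
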